7.2 Method of Treatment Assignment

This study includes a single arm, open-label, multiple ascending dose stage followed by [REDACTED]. Subjects will be assigned to the dose levels in the order described in Section 5.1.1. In the phase 1b stage of the study, enrollment of alternating concurrent dosing cohorts will be facilitated by IVRS. [REDACTED] [REDACTED]. The treatment assignment date is to be documented in the subject's medical record and on the enrollment case report form (CRF).

7.3 Blinding

This is an open-label study; blinding procedures are not applicable.

7.4 Dose Modification

7.4.1 Phase 1b Dose-cohort Study Escalation/De-escalation

7.4.1.1 Dose Level Review Meetings

After all DLT-evaluable subjects within a cohort have completed the 4-week DLT evaluation period, a DLRM will be held to review data, monitor safety, and make dose change decisions. See [Appendix 3](#) for more details on the DLRM.

7.4.1.2 Definition of Dose Limiting Toxicities for Phase 1b

The DLT evaluation period for each subject is 4 weeks from the first dose of efavaleukin alfa. To be evaluable for a DLT subjects must have received at least 2 doses of efavaleukin alfa or have experienced a DLT within the DLT evaluation period. All subjects who experience a DLT will discontinue study therapy and complete safety follow-up. Dose limiting toxicity events will be used to guide dose escalation decisions and to determine the MTD as described in Section 5.1.1.

The following DLT criteria apply only to the phase 1b part of the study:

- Non-hematological toxicity \geq grade 4 related to efavaleukin alfa. Non-hematological laboratory abnormalities without clinical significance will not be considered DLTs (based upon the investigator's discretion in conjunction with Amgen).
- Hematological toxicity \geq grade 4 related to efavaleukin alfa defined as decreases in peripheral counts (ANC or platelets) persisting longer than 72 hours, as measured by 2 separate results, that are not related to malignant disease relapse, infection, or other etiologies.
- Constitutional events (ie, fever, fatigue) \geq grade 3 that are classified as serious adverse events by the investigator and related to efavaleukin alfa.

- Infection: Infection is considered an expected complication of cGVHD and its treatment. cGVHD itself increases the risk of infection, including life-threatening infection. Therefore only grade 4 or 5 infections considered by the investigator to be related to efavaleukin alfa will be reviewed by the DLRM to determine whether the infection is considered a DLT.

Subjects who develop an uncontrolled grade 4 life-threatening infection (eg, sepsis, ARDS), as assessed by the investigator, will discontinue efavaleukin alfa and remain in the study for safety follow-up (see Section 9.1.5).

After completing the 4-week DLT evaluation period, phase 1b subjects will be evaluated by standard safety reporting.

[figure not shown]
7.4.2 Dosage Adjustments, Delays, Rules for Withholding or Restarting, Permanent Discontinuation

7.4.2.1 Amgen Investigational Product: Efavaleukin Alfa

The reason for dose change of efavaleukin alfa is to be recorded on each subject's CRF.

7.4.2.1.1 Phase 1b

Dose adjustment of efavaleukin alfa for individual subjects is not allowed until the [REDACTED] is determined. The Medical Monitor should be informed of withholding of efavaleukin alfa for acute clinical events such as acute infection or major surgery. Once the [REDACTED] dose is determined, all phase 1b subjects may continue study therapy at the [REDACTED] dose and frequency (at the discretion of the Sponsor, following discussion and agreement between the principal investigator and medical monitor) and will be subject to the dose adjustment guidelines in Section 7.4.2.1.2. A subject experiencing worsening of cGVHD that requires the addition of new immunosuppressive medication(s) at any time during the study or initiation of an increase in systemic corticosteroid dose above baseline after week 4 of the study (at the discretion of the treating investigator) will be deemed a treatment failure. These subjects will discontinue treatment and will have a safety follow-up visit (see Section 9.1.5).

7.4.3 Hepatotoxicity Stopping and Rechallenge Rules

Elevated hepatic laboratory values may be observed in subjects with cGVHD who have hepatic involvement. In the phase 1b part of the study, the Medical Monitor should be consulted regarding management of subjects whose abnormal hepatic laboratory values are, in the opinion of the Investigator, attributable to underlying cGVHD. Subjects in the

7.5 Preparation/Handling/Storage/Accountability

Guidance and information on preparation, handling, storage, accountability, destruction, or return of the investigational product during the study are provided in the IPIM.

7.6 Treatment Compliance

Subjects will receive the SC doses of **efavaleukin alfa** at the research facility administered by qualified study personnel for the duration of the study.

7.7 Treatment of Overdose

The effects of overdose of this product are not known.

7.8 Prior and Concomitant Treatment

Throughout the study, investigators may prescribe any concomitant medications or treatments deemed necessary to provide adequate supportive care except for those listed in Section 7.1.7.

All other therapies including steroids, other immunosuppressive medications, prophylactic therapies for infections, and other medications considered supportive care for GVHD will not be provided or reimbursed by Amgen (except if required by local regulation). The investigator will be responsible for obtaining these therapies.

7.8.1 Prior Treatment

[figure not shown]
Prior therapies that were being taken from 12 weeks prior to enrollment through the first dose of investigational product should be collected. Collect complete prior therapy history for GVHD. For prior therapies, collect therapy name, indication, dose, unit, frequency, route, start date and if applicable, stop date.

7.8.2 Concomitant Treatment

Concomitant therapies are to be collected from first dose of investigational product through safety follow-up in the source documents and the eCRF.

For all therapies, collect therapy name, indication, dose, unit, frequency, route, start date, and stop date.

7.8.2.1 Corticosteroids

7.8.2.2 Other Immunosuppressive Medications

Subjects will continue other systemic immunosuppressive background therapies (eg, tacrolimus, sirolimus, MMF, ECP) concomitantly with efavaleukin alfa. Addition or substitution of systemic immunosuppressive therapies beyond dose adjustments to maintain therapeutic levels will be considered a treatment failure. Dose reductions in background therapy are not allowed in the first 8 weeks of the study but may be reduced thereafter in responders at the discretion of the investigator. Disease flares during immunosuppressant taper will not be counted as GVHD progression or treatment failure if the subject can be managed by return to the baseline immunosuppressant dose. Topical immunosuppressant (ie, mouthwash, eye drops, genitourinary ointments) are allowed at the discretion of the investigator.

7.8.2.3 Prophylaxis for Infection

Prophylaxis for infection, including routine viral bacterial and fungal prophylaxis (ie, Bactrim, acyclovir, azole fungals), will be managed according to institutional guidelines. Antimicrobial treatment including antivirals, antibiotics and antifungals will be left to the discretion of the investigator.

7.8.2.4 Other Allowed Therapies

Supportive medications in accordance with standard practice (such as emesis, diarrhea, red blood cell [RBC] or neutrophil growth factors) are permitted per investigator discretion. Other allowed therapies include medications considered supportive care or prophylactic therapy for cGVHD including but not limited to ursodeoxycholic acid, INH, azithromycin, and montelukast.

8. Discontinuation Criteria

Subjects have the right to withdraw from investigational product and/or other protocol-required therapies, protocol procedures, or the study as a whole at any time and for any reason without prejudice to their future medical care by the physician or at the institution.

The investigator and/or sponsor can decide to withdraw a subject(s) from investigational product, device, and/or other protocol-required therapies, protocol procedures, or the study as a whole at any time prior to study completion for the reasons listed in Sections 8.1, 8.2.1, and 8.2.2.

8.1 Discontinuation of Study Treatment

Subjects can decline to continue receiving investigational product and/or other protocol-required therapies or procedures at any time during the study but continue participation in the study. If this occurs, the investigator is to discuss with the subject the appropriate processes for discontinuation from investigational product or other protocol-required therapies and must discuss with the subject the possibilities for continuation of the Schedule of Activities (see [Table 2-1](#), [Table 2-2](#), [Table 2-3](#), [Table 2-4](#), [Table 2-5](#), [Table 2-6](#), [Table 2-7](#), and [Table 2-8](#)) including different options of follow-up (eg, in person, by phone/mail, through family/friends, in correspondence/communication with other treating physicians, from the review of medical records) and collection of data, including endpoints, adverse events, and disease-related events, as applicable and must document this decision in the subject's medical records. Subjects who have discontinued investigational product and/or other protocol-required therapies or procedures should not be automatically removed from the study. Whenever safe and feasible, it is imperative that subjects remain on-study to ensure safety surveillance and/or collection of outcome data.

Subjects may be eligible for continued treatment with Amgen investigational product(s) and/or other protocol-required therapies by a separate protocol or as provided for by the local country's regulatory mechanism, based on parameters consistent with [Appendix 3](#).

Reasons for removal from protocol-required investigational product(s) or procedural assessments include any of the following:

- Decision by Sponsor
- Lost to follow-up
- Death
- Ineligibility determined
- Protocol deviation
- Non-compliance
- Adverse event
- Subject request
- cGVHD progression
- Requirement for alternative therapy
- Protocol-specified reasons as described in Section [7.4.1.2](#) and Section [7.4.2.1.2](#)
- Pregnancy

8.2 Discontinuation From the Study

Withdrawal of consent for a study means that the subject does not wish to receive further protocol-required therapies or procedures, and the subject does not wish to or is unable to continue further study participation. Subject data up to withdrawal of consent will be included in the analysis of the study, and where permitted, publicly available data can be included after withdrawal of consent. The investigator is to discuss with the subject appropriate procedures for withdrawal from the study and must document the subject's decision to withdraw in the subject's medical records.

If a subject withdraws from the study, he/she may request destruction of any samples taken and not tested, and the investigator must notify Amgen accordingly (see [Appendix 6](#) for further details). Refer to the Schedule of Activities for data to be collected at the time of study discontinuation and follow-up and for any further evaluations that need to be completed.

8.2.1 Reasons for Removal From Washout, Run-in or Invasive Procedures

Not applicable.

8.2.2 Reasons for Removal From Study

Reasons for removal of a subject from the study are:

- Decision by sponsor
- Withdrawal of consent from study
- Death
- Lost to follow-up

8.3 Lost to Follow-up

A subject will be considered lost to follow-up if he or she repeatedly fails to return for scheduled visits and is unable to be contacted by the study site.

The following actions must be taken if a subject fails to return to the clinic for a required study visit:

- The site must attempt to contact the subject and reschedule the missed visit as soon as possible and counsel the subject on the importance of maintaining the assigned visit schedule and ascertain whether or not the subject wishes to and/or is able to continue in the study.
- In cases in which the subject is deemed lost to follow-up, the investigator or designee must make every effort to regain contact with the subject (where possible, 3 telephone calls and, if necessary, a certified letter to the subject's last known mailing address or local equivalent methods). These contact attempts are to be documented in the subject's medical record.
- If the subject continues to be unreachable, he/she will be considered to have withdrawn from the study with a primary reason of lost to follow-up.

- For subjects who are lost to follow-up, the investigator can search publicly available records [where permitted]) to ascertain survival status. This ensures that the data set(s) produced as an outcome of the study is/are as comprehensive as possible.

9. Study Assessments and Procedures

Study procedures and their time points are summarized in the Schedule of Activities (see [Table 2-1](#), [Table 2-2](#), [Table 2-3](#), [Table 2-4](#), [Table 2-5](#), [Table 2-6](#), [Table 2-7](#), and [Table 2-8](#)).

As protocol waivers or exemptions are not allowed if an enrolled subject is subsequently determined to be ineligible for the study, this must be discussed with the sponsor immediately upon occurrence or awareness to determine if the subject is to continue or discontinue study treatment.

Adherence to the study design requirements, including those specified in the Schedule of Activities, is essential and required for study conduct.

9.1 General Study Periods

9.1.1 Screening, Enrollment and/or Randomization

The general study assessments and procedures will apply to subjects in both the phase 1b and [REDACTED] portions of the study.

Informed consent must be obtained before completing any screening procedure or discontinuation of standard therapy for any disallowed therapy. After the subject has signed the informed consent form, the site will register the subject in the IVRS/IWRS and screen the subject in order to assess eligibility for participation. The screening window is up to 28 days.

[figure not shown]
[figure not shown]
All screening evaluations must be completed and reviewed to confirm that potential subjects meet all eligibility criteria. The investigator will maintain a screening log to record details of all subjects screened and to confirm eligibility or record reasons for screening failure, as applicable.

If a subject has not met all eligibility criteria at the end of the screening period, the subject will be registered as a screen fail. Screen fail subjects may be eligible for re-screening 2 times in consultation with Amgen medical monitor.

Rescreen subjects must first be registered as screen failures in IVRS/IWRS and subsequently registered as rescreens. Once the subject is registered as rescreened, a new 28-day screening window will begin. Subjects will retain the same subject identification number assigned at the original screening. If the rescreening period begins more than 28 days after the original signing of the informed consent form, all screening procedures, including informed consent, must be repeated.

9.1.2 Treatment Period

Visits will occur per the Schedule of Activities (see [Table 2-1](#), [Table 2-2](#), [Table 2-3](#), [Table 2-4](#), [Table 2-5](#), [Table 2-6](#), [Table 2-7](#), and [Table 2-8](#)). In the phase 1b part of the study, visits may be completed within a visit window of \pm 1 day through the week 4 visit. After the week 4 visit, the visit window may increase to \pm 3 days from the scheduled visit date for those phase 1b subjects on Q2W dosing and \pm 2 days from the scheduled dose date for those subjects on QW dosing.

9.1.3 Progressive Disease Visit

A progressive disease visit should be performed any time during the study, if the investigator suspects progressive disease and the subject is experiencing worsening of cGVHD that requires the addition of new immunosuppressive medication(s) or initiation of an increase in systemic corticosteroid dose above baseline after week 4 of the study. Efavaleukin alfa should be discontinued, followed by an end of treatment visit (see Section [9.1.4](#)) and a safety follow-up visit (see Section [9.1.5](#)).

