9.1.4 End of Treatment

Subjects discontinuing treatment prior to week 52 for any reason (see Section [8.1](#)) will be asked to complete an End of Treatment visit within a window of \pm 7 days of the next regularly scheduled visit after the last dose of efavaleukin alfa, consisting of all assessments included in the week 52 visit according to the Schedule of Activities (see [Table 2-2](#)). If the End of Treatment visit for a subject occurs $<$ 7 days after a progressive

disease visit, then the procedures completed at the End of Treatment visit should only be those NOT performed at the progressive disease visit.

For phase 1b subjects participating in the extended dosing period, subjects discontinuing treatment prior to week **102** or week **103** will be asked to complete the EOET visit within a window of + 7 days of the next regularly scheduled visit after the last dose of efavaleukin alfa, consisting of all assessments included in week **104** visit according to the Schedule of Activities (see [Table 2-3](#)). Subjects continuing treatment after week **104** but discontinuing treatment before week **258** (Q2W dosing) or week **259** (QW dosing) will be asked to complete an EOET visit within a window of \pm 7 days of the next regularly scheduled visit after the last dose of efavaleukin alfa, consisting of all assessments included in the week **260** visit according to the Schedule of Activities (see [Table 2-6](#)). If the EOET visit for a subject occurs < 7 days after a progressive disease visit, then the procedures completed at the EOET visit should only be those NOT performed at the progressive disease visit.

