**PD assessments include but are not limited to:**

[REDACTED]

[REDACTED]

[figure not shown]
[REDACTED] Due to the skewed distribution of PD data, mean, standard deviation and standard error will be estimated based on log-transformed data, and the estimates will be back-transformed and presented, which are equivalent to geometric mean, geometric standard deviation and geometric standard error.

To maintain the integrity of PD results, data collected at an end of treatment or end of extended treatment visit which is completed outside the upper limit of protocol defined window (> 9 days after the last dose date for QW cohorts and > 16 days for Q2W cohorts) will not be included in the analysis. In addition, data collected at a visit after skipping one or more consecutive doses prior to that visit will be also excluded from analysis (the same window will be used as above i.e. (> 9 days after the last dose date for QW cohorts and > 16 days for Q2W cohorts).

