## Appendix G. Analytical Windows

The last visit with non-missing assessment prior to first dose will be defined as a baseline visit (unless specified otherwise) and the analysis visit name will be “Baseline”. For any visit up to Day 1 pre-dose which is not a baseline visit, the analysis visit will be ‘Pre-Analysis’. For Day 1 post-dose visits, and safety follow-up visit, the analysis visit will be same as the scheduled visit. For any unscheduled visit post safety follow-up visit, the analysis visit will be considered as safety follow-up visit. For post-dose assessments on Day 29 (the day corresponding to Week 4 dosing) and Day 113 (the day corresponding to week 16 dosing), the analysis visit will be same as the scheduled visit. Remaining visits (scheduled visit, unscheduled visit, progressive disease visit, or end of treatment visit) after Day 1 for any assessment will be mapped to the analysis visit based on visit windows defined in the tables below for that assessment. Only visits applicable for that assessment and phase of the study as per the Schedule of Activities tables in the study protocol will be considered for analysis.

Data collected through central lab and local lab will both be mapped into analysis visit windows. The local lab data can only be used in analysis when there is no central lab data available in the analysis visit window.

If more than one visit with non-missing data falls within an analysis visit window, the visit closest to the target day will be considered for analysis. If two visits are equidistant from the target day, the latest visit (or time if on the same day) will be considered. If more than one evaluation has same date and time (for chemistry, hematology or pharmacodynamics results), the value with the smallest accession number will be considered.

Analysis visit windows for selected assessments are included in tables below. For remaining assessments, no visit window will be applied. Day 29 and Day 113 used in Study day window calculation in the tables below is the respective study day when Week 4 dose and Week 16 dose was received. If that dose is missing, then 29 and 113 is used for respective calculation.

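### Pharmacodynamic samples drawn after a treatment failure has begun rescue immunosuppression can enter the by-dose summaries, because the SAP screens them only on days since last dose

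*Protocol*

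**What the plan says.** **Trigger.** Protocol 9.1.3 calls for a progressive disease visit when the investigator suspects progression and this condition holds: "the subject is experiencing worsening of cGVHD that requires the addition of new immunosuppressive medication(s) or initiation of an increase in systemic corticosteroid dose" (for steroids, a dose higher than at baseline, once week 4 has passed). Protocol 7.4.2.1.1 gives the same events as its definition of failure: such a subject "will be deemed a treatment failure. These subjects will discontinue treatment and will have a safety follow-up visit".

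**Next visit.** Under 9.1.3, "Efavaleukin alfa should be discontinued, followed by an end of treatment visit". Protocol 9.1.4 describes that visit as "consisting of all assessments included in the week 52 visit according to the Schedule of Activities", held within plus or minus "7 days of the next regularly scheduled visit after the last dose of efavaleukin alfa". If it falls less than 7 days after the progressive disease visit, "then the procedures completed at the End of Treatment visit should only be those NOT performed at the progressive disease visit".

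**Sample.** Protocol 9.2.6 uses the lymphocyte-subset sample to measure Treg, Tcon and NK cells. Week 52 is a pharmacodynamic analysis visit in SAP Appendix G.

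**Analysis.** Appendix G states: "Remaining visits (scheduled visit, unscheduled visit, progressive disease visit, or end of treatment visit) after Day 1 for any assessment will be mapped" to analysis visits by study-day window. SAP 9.7.1.2 has two readable exclusions. The first begins "To maintain the integrity of PD results, data collected at an end of treatment or end of extended treatment visit" and removes samples more than 9 days (QW) or 16 days (Q2W) after the last dose. The second applies the same limits to visits that follow skipped doses. Summaries are by dose level (Protocol 10.4.2.4.2), with means computed on the log scale (SAP 9.7.1.2).

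**The concern.** The exclusions in SAP 9.7.1.2 are there to keep the summaries representative of the assigned dosing. A sample drawn after rescue has begun may also fail to represent it, since it may reflect a second immunosuppressant or a higher steroid dose acting on the cells being counted. No readable rule excludes, flags or separately reports such a sample.

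Affected samples come only from subjects who failed treatment, so any distortion is related to outcome. Cohorts are small, and one value carries between a sixth and a third of the log-scale mean. At stake is whether the reported Treg, Tcon and NK profile by dose can be read as the effect of efavaleukin alfa plus stable background therapy.

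**Working it through.** The plan gives no figure to reproduce on this point. The check has three parts: whether the sample exists, whether it passes the screen, and how far one value moves a cohort mean.

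**1. Does the end-of-treatment visit carry a sample?** The lymphocyte row of Protocol Table 2-2 is broken in the extracted text, but it shows 28 marks. Appendix G lists these pharmacodynamic weeks between 6 and 52: weeks 6–12 (7), weeks 14, 16, 17 and 18 (4), even weeks 20–50 (16), and week 52 (1). The sum is 7 + 4 + 16 + 1 = 28. The match supports a week 52 sample and, if it is right, no lymphocyte sample at the progressive disease visit. In that case the less-than-7-days provision in 9.1.4 would not remove the sample from the end-of-treatment visit.

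**2. Does the screen catch it?** The inputs are visit spacing (weekly for QW; for Q2W, weekly before week 18 and every two weeks from week 18, Table 2-2 footnote g), the ±7-day window (Protocol 9.1.4), and the limits of 9 and 16 days (SAP 9.7.1.2). Days after last dose = days to next scheduled visit ± 7.

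| Regimen | Visit can fall on | Kept | Excluded | Share kept |
|---|---|---|---|---|
| QW | 7 ± 7 = days 0–14 | 0–9 | 10–14 | 10 of 15 |
| Q2W before week 18 | 7 ± 7 = days 0–14 | 0–14 | none | 15 of 15 |
| Q2W from week 18 | 14 ± 7 = days 7–21 | 7–16 | 17–21 | 10 of 15 |

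An end-of-treatment visit held on schedule (day 7 for QW, day 7 or 14 for Q2W) always passes. At the extreme, if rescue began the day after the last dose, a kept sample could follow 9 − 1 = 8 days of it (QW) or 16 − 1 = 15 days (Q2W from week 18).

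Appendix G then keeps the value closest to the target day. For Q2W from week 18 through week 52, an on-time visit falls on the next target day, so it would usually be the value kept. For QW this happens when the next visit is a pharmacodynamic week, for example weeks 6–11.

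**3. How far can one value move the mean?** If one of n subjects has its value multiplied by f, the cohort geometric mean is multiplied by f^(1/n). Protocol 5.1.1 gives n as 3 to 6 DLT-evaluable subjects. The factor f is an assumption.

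| f (assumed) | n = 6 | n = 3 |
|---|---|---|
| 0.5 | 0.89 | 0.79 |
| 1.5 | 1.07 | 1.14 |
| 2.0 | 1.12 | 1.26 |

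A doubling raises the mean at that visit by 12% (n = 6) to 26% (n = 3). A halving lowers it by 11% to 21%.

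**The case against.** The strongest reply is that the sequence is not documented. Section 9.1.3 says that rescue is required or initiated; it does not date the first rescue dose against the end-of-treatment sample. Protocol 7.8.2.1 (Corticosteroids) shows a heading without text, and section 7.4.2.1.2 is cited but not visible, so an ordering rule could exist there. This stands: rescue effects can enter the summaries, but the documents do not show that they do. It does not close the gap, because nothing readable requires the sample to be drawn first.

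Second, the effect may be small. Protocol 7.1.7 bars starting recombinant IL-2, ECP, T-cell-depleting, IL-2-signalling-targeted and Treg-expanding therapies during participation. Steroids and other immunosuppressants remain, and these are what define failure. Each failure contributes at most one end-of-treatment value, at one analysis visit. About 30 escalation subjects over five planned cohorts is 6 each, so n = 6 is the planned case and n = 3 the lower bound. All of this stands.

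Third, exclusion is itself selective. Protocol 7.8.2.2 lets responders reduce background therapy after week 8 and their samples stay in, while failures' late samples would come out. This too stands, and it is why the all-sample summary belongs beside the main one.

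A reader might go further in three directions that the documents do not support:

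- **Dose selection is biased.** SAP 3.1 cancels the expansion cohort and phase 2, and SAP 10 drops the phase 1b interim analysis. What remains is descriptive.
- **This is a larger problem than missed doses.** Nothing in the documents compares the two.
- **The longer Q2W limit lets in more such samples and so distorts the QW versus Q2W comparison.** The share of the window kept is 15 of 15 days only before week 18. From week 18 it is 10 of 15, the same as QW.

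**Conclusion.** The gap is real and limited. A lymphocyte-subset sample taken at the end-of-treatment or end-of-extended-treatment visit, or at another mapped visit, after a treatment failure has started rescue can be kept under either dosing regimen and reported as an effect of that dose at that week. The consequence is confined to the final descriptive pharmacodynamic results by dose.

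The shift of about 12% to 26% rests on an assumed 2-fold increase in one subject and on cohorts of 6 down to 3; the documents supply neither size nor direction. The conclusion also rests on the readable text of SAP 9.7.1.2. Parts of that section are redacted, but its exclusion paragraph is legible.

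**What to change.** Add a third rule to SAP 9.7.1.2. It should apply to subjects who meet the protocol's treatment-failure definition: a new systemic immunosuppressant for worsening cGVHD at any time, or a systemic steroid increase above baseline for worsening cGVHD after week 4. Their pharmacodynamic samples dated after the start of that medication on the concomitant medication CRF are flagged, listed and left out of the main by-dose summary. The all-sample summary is shown as a sensitivity analysis.

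The rule should not be triggered by any steroid increase at all. That would discard later samples from subjects who had an increase before week 4, or a short course for a reaction of the kind described in Protocol 3.2.3, and who stayed on drug.

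Two sets of passages should be reconciled at the same time. SAP 9.7.1.2 presents 9 and 16 days as the protocol's upper limit, whereas the ±7-day window in Protocol 9.1.4 reaches 14 and 21 days. Protocol 7.4.2.1.1 names only a safety follow-up visit after failure, whereas 9.1.3 also names an end-of-treatment visit.

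The cost is a short SAP addition and a date flag built from data already collected (Protocol 7.8.2; Table 2-2 footnote e). A few late values from failures leave the main summary, and that loss is related to outcome; the all-sample summary shows what difference it makes.
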